Amendment 1	30-May-2018	
The amendment is largely based on the changes made in the Clinical Trial Protocol Amendment 5 (released 17-Jan-2018). More details about the rationale of the major changes are given in the section "Amendment 1". In summary, the following changes are implemented:
 
• The primary analysis will be conducted after all patients have completed the Week 26 assessments or discontinued from the study; changes are made in multiple sections with details given in Section 2.9.• Modified key secondary objective in Section 2.1.2 and updated analysis accordingly in Section 2.6.1.• Updated testing strategy for multiplicity due to the change in key secondary objective.• Sample size has been updated in Section 2.10.• Added the estimand statements in Section 2.1.• Modified the handling of missing items when calculating the ACQ-7 score and clarified the handling of missing ACQ-7 score for ACQ-responder analysis in Section 2.6.1.1.2.• Added ACQ-5 in Section 2.6.2.3.• Modified the handling of missing items in the AQLQ overall and domain scores in Section 2.6.2.8.• Added exposure-adjusted analyses of adverse events in Section 2.7.2.• Changed the analysis plan for glucose and potassium data.• Removed the logistic regression analysis for percentage of patients with at least one asthma exacerbation by exacerbation category and patients who permanently discontinued study medication due to asthma exacerbations in Section 2.6.2.7.• Extended the post-morning dose time window restriction in handling of spirometry measurements from 10-13 hours to 8-13 hours for b.i.d. regimens in Section 2.6.1.1.• Modified the multiple imputation method in tipping point analysis from monotone method to fully conditional specification method in Section 2.6.1.4 and Section 16.1.9.6.• Combined the imputation steps into one step for the ACQ responder analysis in Section 2.6.2.3 and Section 16.1.9.6.• Removed SAS code from SAP in Section 16.1.9.6 and included them in TFLs.• Removed the definitions of AEs of special interest from Section 2.7.2.• Updated criteria for Hy's law as per current guideline.• Added Section 3 for specifying analyses that will be reported outside of CSR.• Added Japanese and Chinese patients in subgroup analyses in Section 3.1.

Version	Date	Changes
		
■ [REDACTED]
 
• Added the analysis of add-on effect of indacaterol to existing MF treatment for trough FEV₁ in Section 2.6.2.2 and asthma exacerbations in Section 2.6.2.7.• Re-organized Section 2.6.2.7 to place the detailed analysis under each parameter of interest.• Added the AE summary based on incidence rates per 100 patient-years in Section 2.7.2.• Deleted several safety endpoints for time to event analyses in Section 2.7.2.• Added major protocol deviations list in Section 16.1.9.2.• Some other minor changes.• Added notable criterion for Magnesium.
Amendment 2	27-Sep-2018	
• Updated action plan if model fails to converge in Section 2.6.1.2 and 16.1.9.6.• Added non-parametric test exploration in case of non-convergence or highly skewed data in Section 2.6.2.4 and 2.6.2.5.• Outlined the sensitivity analyses to be done with and without a site which was identified to have lack of quality issues in Section 1.• Correction, removed "The responder analysis will use the same imputed datasets as that of ACQ-7", as for ACQ-5 same analyses is done as for ACQ-7 but not same imputed dataset as multiple imputation is for each score separately in Section 2.6.2.3.• Correction of PD-ID in Section 16.1.9.2.• Changed notable criteria for Magnesium to SI unit for consistency in Section 16.1.9.5.• Added the details of least squares mean computation in Section 16.1.9.6.• Added additional analyses on potassium excluding all flagged data in Section 2.7.3.• Added the definition of implausible value for FEV₁ in Section 2.6 and 16.1.9.3.

2.7	Safety evaluation.....	25
2.7.1	Serious asthma outcomes.....	25
2.7.2	Adverse events.....	25
2.7.3	Laboratory data.....	27
2.7.4	Vital signs.....	30
2.7.5	Electrocardiogram (ECG).....	30
	[REDACTED].....	31
	[REDACTED].....	31
	[REDACTED].....	31
2.9	Interim analysis.....	32
2.9.1	Data Safety Monitoring Board (DMC).....	32
2.9.2	Primary analysis after all patients have completed at least 26 weeks treatment.....	32
2.10	Sample size calculation.....	33
3	Analyses to be reported outside of CSR.....	33
3.1	Subgroup analyses.....	33
	[REDACTED].....	34
	[REDACTED].....	34
	[REDACTED].....	35
	[REDACTED].....	35
	Clinical Study Report - Appendix 16.1.9 Documentation of statistical methods.....	37
16.1.9.1	Introduction.....	37
16.1.9.2	Major protocol deviations and other exclusion criteria.....	37
16.1.9.3	Assessment windows, baseline and post-baseline definitions, missing data handling.....	39
16.1.9.3.1	Data pooling and assessment windows.....	39
16.1.9.3.2	Baseline measurements.....	39
16.1.9.3.3	Post-baseline measurements.....	41
16.1.9.4	Laboratory parameters – direction of interest and definition of clinically notable values.....	42
16.1.9.5	Vital signs and ECG – definition of clinically notable values.....	44
16.1.9.6	Statistical methodology and assumptions.....	45

Amendment 1

This amendment of the statistical analysis plan (SAP) is largely based on the changes made in the Clinical Trial Protocol Amendment 5 (released 17-Jan-2018). The rationale of the major changes in protocol is provided in the following.

Amendment Rationale

Conduct primary analysis after all patients have completed at least 26 weeks treatment:

An interim database freeze will be conducted to perform the primary analysis. The database for primary analysis will contain all data up to the Data Lock Point (DLP), which is defined as the date when all patients complete Week 26 (V207) assessments or withdraw from the study. For patients who are ongoing at the time of interim database freeze, the database will include all data available until the last completed visit.

Primary analysis includes primary and key secondary endpoints as well as other pre-specified endpoints at Week 26. [REDACTED]

Safety data will also be summarized.

In terms of reporting, two separate clinical study reports (CSRs) will be written. CSR 1 will base on the interim database freeze and CSR 2 on the final database lock. A dedicated unblinded team will be involved in CSR 1 related activities. In order to maintain the integrity of the study data, a separate blinded team will continue the study until its completion.

Modification of analysis of key secondary endpoint, ACQ-7:

The key secondary objective has been modified to demonstrate the superiority of add-on indacaterol (QAB149) 150 µg by demonstrating superiority of QMF (150/160 and 150/320 µg combined) to mometasone furoate doses (MF, 400 µg and 800 µg combined) in terms of Asthma Control Questionnaire (ACQ-7) after 26 weeks of treatment. The add-on effect of indacaterol will be tested only if the individual treatment comparisons are significant for the primary endpoint (i.e., there is evidence of efficacy of both doses of QMF over respective MF doses in terms of lung function).

Sample size is re-calculated based on updated analysis and multiplicity adjustment. As a result, a more modest sample size is needed to establish efficacy while providing sufficient safety exposure for QMF149. Assuming 10% dropout, the calculation shows that the sample size of 2000 patients (i.e., 400/arm) will provide 94% power for primary endpoint trough FEV₁ and 85% power for key secondary endpoint ACQ-7.

1 Introduction

This document contains details of the statistical methods that will be used in the phase III clinical trial CQVM149B2301. This study is designed to evaluate the efficacy and long term safety of two different doses of QMF149 (QMF149 150/160 µg and QMF149 150/320 µg via Concept1) over two respective mometasone furoate (MF) doses (i.e., total daily doses of MF 400 µg and MF 800 µg via Twisthaler®) in poorly controlled asthmatic patients as determined by pulmonary function testing and effects on asthma control.

Data will be analyzed according to Section 9 of the study protocol. The primary analysis will be conducted using all data up to the Data Lock Point (DLP), which is defined as the date when all patients have completed the assessments after at least 26 weeks of treatment (Visit 207) or prematurely withdrawn from the study. In particular for efficacy analysis, each patient's data until the last available study visit (scheduled or unscheduled) prior to the DLP will be included. For safety analysis, data up the DLP will be included too. This will include all planned analyses presented in this SAP.

Two separate CSRs will be published:

- Primary Analysis CSR: To support analyses once all patients have completed the assessments at least 26 weeks of treatment (Visit 207) or prematurely withdrawn from the study.
- Full CSR: To support analyses once all patients have completed the assessments after 52 weeks of treatment (Visit 214) plus follow-up (Visit 301) or prematurely withdrawn from the study.

This SAP is valid for analyses of both CSRs.

Important information is given in the following sections and details are provided, as applicable, in [Appendix 16.1.9](#).

Subgroup analyses will be performed for adolescent patients (12 - 17 years old) and for specific countries (e.g., China, Japan). These analyses will be identified in the tables, figures, and listings shell document. For tables presenting results from statistical models, the treatment effects in adolescent patients will be derived from the treatment x age subgroup interaction term by including all patients in the analysis. This is different than the country-specific subgroup analyses where only the patients of the respective country will be included.

In consideration of the lack of quality control applied by the PI on study source data, a sensitivity analysis will be performed by assessing for primary, key secondary endpoints and AEs/SAEs both with and without patient data from the following site in order to evaluate whether the data from this site have an impact on overall results:

██████████.

2 Detailed statistical methodology

2.1 Study objectives

Section 2 of the study protocol lists the following primary, key secondary, other secondary ██████████ objectives.

2.1.1 Primary objective

The primary objective is to demonstrate the superiority of either QMF149 150/160 µg delivered via Concept1 o.d. (in the evening) to MF 400 µg o.d. (in the evening) delivered via Twisthaler® or QMF149 150/320 µg delivered via Concept1 o.d. (in the evening) to MF 800 µg delivered via Twisthaler® (delivered as 400 µg b.i.d.) in terms of trough FEV₁ after 26 weeks of treatment in patients with asthma.

The primary estimand can be described by defining the following components:

- **Population:** adolescent (12-17 years old) and adult asthmatic patients (≥18 years old) receiving medium or high dose inhaled corticosteroids (ICS) or low dose ICS/long acting beta-2 agonist (LABA) combination
- **Variable:** trough FEV₁ after 26 weeks of treatment
- **Summary measures:** mean differences between treatment groups for each MF dose level (QMF149 150/160 µg vs MF 400 µg; QMF149 150/320 µg vs MF 800 µg).
- **Intervention effect of interest:** add-on effect of indacaterol evaluated at each MF dose level, based on randomized treatments, if all patients had remained on randomized treatment for 26 weeks, with the following post-randomization events accounted for by assessing:
 - **Intake of non-study drugs with effect on FEV₁:** the effect outside of period of worsening disease that necessitates non-study medication
 - **Discontinuation of study treatment prior to week 26:** hypothetical on-treatment week 26 FEV₁ value
 - **Week 26 FEV₁ measurements taken outside of the 22-25 hour post-evening (or 8-13 hour post morning for b.i.d. regimens) dose time window:** hypothetical on-treatment week 26 FEV₁ value

2.1.2 Key secondary objective

The key secondary objective is to demonstrate the superiority of QMF149 (150/160 µg and 150/320 µg combined) to MF (400 and 800 µg combined) in terms of Asthma Control Questionnaire (ACQ-7) after 26 weeks of treatment in patients with asthma.

The key secondary estimand can be described by defining the following components:

- **Population:** adolescent and adult asthmatic patients receiving medium or high dose ICS or low dose ICS/LABA combination
- **Variable:** ACQ-7 after 26 weeks of treatment
- **Summary measure:** mean treatment difference between QMF149 and MF (i.e. average of differences between [QMF149 150/160 µg vs MF 400 µg] and [QMF149 150/320 µg vs MF 800 µg]).
- **Intervention effect of interest:** add-on effect of indacaterol on MF irrespective of the dose level of MF, based on randomized treatments, if all patients had remained on randomized treatment for 26 weeks, with the following post-randomization event accounted for by assessing:

- **Discontinuation of study treatment prior to week 26:** hypothetical on-treatment week 26 ACQ-7 value

2.1.3 Secondary objectives

Secondary objectives are to compare a) QMF149 150/160 µg o.d. delivered via Concept1 compared to MF 400 µg o.d. delivered via Twisthaler® and b) QMF149 150/320 µg o.d. delivered via Concept1 compared with MF 400 µg b.i.d. delivered via Twisthaler® in terms of:

[figure not shown]
- Trough FEV₁ at Week 52
- Pre-dose FEV₁ (defined as the mean of -45 min and -15min FEV₁ values pre-evening dose) at Week 4 and Week 12
- FEV₁, Forced Vital Capacity (FVC) and Forced Expiratory Flow between 25% and 75% of FVC (FEF₂₅₋₇₅) over 52 weeks
- Morning and Evening Peak Expiratory Flow Rate (PEF) over 26 and 52 weeks of treatment
- Asthma control as assessed by the ACQ-7 at Week 4, Week 12 and Week 52
- Percentage of patients achieving the minimal important difference (MID) ACQ ≥ 0.5 at Week 26 and Week 52
- Daily e-Diary recordings of the percentage of asthma symptom-free days, no daytime symptoms, the percentage of nights with no nighttime awakenings and the percentage of mornings with no symptoms on awakening over 52 weeks of treatment
- e-Diary recordings of rescue salbutamol/albuterol usage (mean daily, nighttime and daytime use) over 26 and 52 weeks of treatment
- % of rescue medication-free days over 26 and 52 weeks of treatment
- To evaluate the efficacy of in terms of asthma exacerbation-related parameters described here during 52 weeks of treatment. The analysis will be performed by exacerbation category wherever specified. The exacerbation categories are: mild, moderate, severe and moderate or severe:
 - Time to first asthma exacerbation by exacerbation category
 - Time to first hospitalization for asthma exacerbation
 - Annual rate of asthma exacerbations by exacerbation category
 - Duration in days of asthma exacerbations by exacerbation category
 - Percentage of patients with at least one asthma exacerbation by exacerbation category
 - Time to permanent discontinuation of study medication due to asthma exacerbations
 - Percentage of patients who permanently discontinued study medication due to asthma exacerbations
 - Total amounts of systemic corticosteroids (in doses) used to treat asthma exacerbations
- Quality of life as assessed by Asthma Quality of Life Questionnaire (AQLQ) over 52 weeks

Furthermore, as additional secondary objectives, QMF149 150/320 µg o.d. delivered via Concept1 will be compared with salmeterol xinafoate /fluticasone propionate 50/500 µg via Accuhaler® for all the listed secondary endpoints above as well as the following ones:

- Trough FEV₁ measured after 26 weeks of treatment
Trough FEV₁ will be tested for non-inferiority versus salmeterol/fluticasone 50/500 µg. If non-inferiority criteria are met, this will be tested for superiority.
- Asthma control as assessed by the ACQ-7 after 26 weeks treatment.

The following safety and tolerability endpoints will be evaluated for all treatment comparison groups:

- Cumulative incidence of the composite endpoint of serious asthma outcomes (i.e. asthma-related hospitalization, asthma-related intubation, or asthma-related death) over 52 weeks of treatment
- Adverse events, vital signs, ECG and laboratory analysis (hematology, blood chemistry including glucose and potassium, urinalysis, evening plasma cortisol) over 52 weeks of treatment

2.1.5 Changes in the conduct of the study or planned analyses

The logistic regression analysis for the percentage of patients with at least one asthma exacerbation by exacerbation category has been removed because of the existence of time to event analysis, which is a more valid approach as it takes into account the event, censoring, and

event/censoring times. The percentages will be presented in the time to event tables. Similarly, the logistic regression for the percentage of patients who permanently discontinued study medication due to asthma exacerbations has been removed.

The restriction on trough FEV₁ measurement (at Visit 201, 207, and 214) time that it has to fall into 10-13 hours post-morning dose time window has been extended to 8-13 hours and only for b.i.d. regimens. This is considered clinically justified based on Seretide[®] dosing interval and expected duration of the bronchodilator effect. The original 10-13 hours post-morning dose time window is considered conservative based on Seretide[®] dosing regimen from the evidence in available literature showing that the bronchodilator effect starts to decrease after 8 hours (Pearlman et al. 1992).

2.2 Analysis sets

The following analysis sets are defined:

- The randomized (RAN) set will consist of all patients who were assigned a randomization number, regardless of whether or not they actually received study medication. Patients in RAN will be analyzed according to the treatment they were randomized to. The RAN set will be used for a summary of patient disposition, demographics and baseline characteristics.
- The Full Analysis Set (FAS) will consist of all patients in the RAN set who received at least one dose of study medication. Following the intent-to-treat principle, patients will be analyzed according to the treatment they were assigned to at randomization. The FAS will be used in the analysis of all efficacy variables.
- The Per-Protocol set (PPS) will include all patients in the FAS who did not have any major protocol deviations. Major protocol deviations will be defined in the validation analysis plan prior to database lock and the un-blinding of the study. The list of major protocol deviations is available in [Appendix 16.1.9](#). Patients will be analyzed according to the treatment they received. The PPS will be used for supportive analysis of the primary analysis only.
- The Safety Set will consist of all patients who received at least one dose of study medication including non-randomized patients who received study drug in error. Patients will be analyzed according to the treatment they received. If patients switch double-blind treatment during the study, they will be counted and analyzed only once according to their initial treatment. The safety set will be used in the analysis of all safety variables.

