2.6.1.2 Statistical model, hypothesis, and method of analysis

Primary variable

The primary objective to demonstrate superiority of either QMF149 150/160 µg to MF 400 µg or QMF149 150/320 µg to MF 800 µg in terms of trough FEV₁ after 26 weeks of treatment will be evaluated by testing the following null hypotheses (H₀) versus the alternative hypotheses (H_a):

H₀₁: QMF149 150/160 µg is equal to MF 400 µg

versus

H_{a1}: QMF149 150/160 µg is not equal to MF 400 µg

and

H₀₂: QMF149 150/320 µg is equal to MF 800 µg

versus

H_{a2}: QMF149 150/320 µg is not equal to MF 800 µg

The primary variable, trough FEV₁ at Week 26, will be analyzed using a mixed model for repeated measures (MMRM) on the FAS. The model will contain treatment, age group (12 to 17, or ≥ 18 years), region (Eastern Europe, Western Europe, India, Japan, other Asia, rest of world), visit (Days 2, 184, and 365), and treatment-by-visit interaction as fixed effects with baseline FEV₁ measurement, baseline-by-visit interaction, FEV₁ prior to inhalation and FEV₁ within 15 to 30 min post inhalation of salbutamol/albuterol (components of short acting beta-2 agonist (SABA) reversibility) as covariates, and center nested within region as a random effect. The within-patient correlation will be modeled using an unstructured covariance matrix in the mixed model. The Kenward-Roger approximation will be used to estimate denominator degrees of freedom (Kenward and Roger, 1997).

For the primary analysis, if the model does not converge, data only up to week 26 (i.e., Days 2 and 184) will be used (with unstructured covariance matrix). If still the model fails to converge, compound symmetry covariance matrix will be used. If model still does not converge, the random effects of center will be removed. For the final analysis, if the model does not converge with unstructured covariance matrix, the compound symmetry covariance matrix will be used in the mixed model. If still the model does not converge, the random effects of center will be removed. For both analyses, if the model converges after removing the random center effects, the original model without random center effects will be re-assessed. If the final model for the primary analysis converges without Week 52 data, only summary statistics will be provided for Week 52 data analysis. Restricted maximum likelihood method will be used.

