2.6.1.4 Supportive analyses for the primary objective

As supportive analysis, the same MMRM used in the primary analysis will be also performed on the PPS to assess the treatment effect in protocol adherers.

In addition, the same primary MMRM on the FAS will be performed including all spirometric measures irrespective of single depot corticosteroid injection, other systemic corticosteroid use, or rescue medication use. However, measures taken outside of the 22 – 25 hour post-evening dose window for o.d. regimens (or 8 - 13 hour post-morning dose window for b.i.d. regimens) will be excluded.

As a further sensitivity analysis, a so-called 'tipping point analysis' will be performed for the primary endpoint to evaluate the impact of a deviation from the MAR assumption. The delta-adjusting approach described in Ratitch et al (2013) will be used to find the tipping point, in a spectrum of conservative missing not at random (MNAR) assumptions, at which conclusions change from being favorable to QMF149 to being unfavorable. After such a tipping point is determined, clinical judgment can be applied as to the plausibility of the assumptions underlying this tipping point. This methodology would provide a good picture of what it would take to overturn study conclusions on the basis of varying assumptions about missing data. The basic idea is to first impute the missing Week 26 values using the multiple imputation (MI) method based on the missing at random (MAR) assumption. The imputed Week 26 values for the QMF149 arms are then adjusted by a delta value. A detailed description of the analysis steps is provided in [Appendix 16.1.9](#).

The following ██████████ subgroup analyses for trough FEV₁ using MMRM will be performed (using the appropriate interaction term in the model and additional covariate as a fixed effect if necessary) for the FAS to explore the treatment effect in:

- Age group (12 to 17 years, ≥ 18 years)
- Race (Caucasian, Asian, Black and other)
- Sex (male, female)
- History of asthma exacerbation in the 12 months prior to screening (Yes, No)
- Patients' prior therapies before run-in period (medium dose of ICS, high dose of ICS, and low dose ICS/LABA; see Appendix 11 of the study protocol for the definition of ICS dose levels)
- Pre-bronchodilator FEV₁ in % of predicted FEV₁ at run-in visit 101 (50% to < 60%, 60% to < 85%)
- ACQ-7 at baseline (1.5 - < 2, 2 - < 2.5, ≥ 2.5)

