- OTH08: Patient not having correct run in medication (i.e. 100mcg accuhaler or 125 mcg via MDI inhaler) or dose equivalent
- COMD07: Use of parenteral or oral corticosteroids less than 4 weeks prior to visit 101
- COMD08: Intra muscular corticosteroid less than 3 months prior to Visit 101
- COMD09: Use of Ige inhibitor less than 4 months prior to visit 101
- COMD10: Xanthine's use less than 7 days prior to visit 101
- COMD12: Last LABA washout more than 4 days prior to visit 101 or last ICS wash out more than 7 days before visit 101
- OTH06: Compliance failure of the patient influencing the safety and efficacy data as per investigator judgement
- OTH04: Patient receiving investigational drug other than study drug during the course of the study
- COMD05: Leukotriene antagonists and leukotriene synthesis inhibitors taken less than 7 days prior to visit 101
- COMD06: Use of SABA other than rescue medication, not discontinued at Visit 1
- COMD11: LABA taken less than 48h before Visit 101
- COMD01: Banned asthma related Concomitant medication
- WITH01: More than 5 exacerbation and still on treatment
- WITH02: Adolescent patient experience one severe exacerbation requiring hospitalization (ER>24) and is still on treatment

Exclusions from full analysis set and per-protocol set:

- OTH05: Patient Randomized more than one Trial.
- OTH14: Patient randomized more than once into this trial

Exclusions from full analysis set, per-protocol set, safety set, [REDACTED]:

- OTH02: Patient randomized but did not receive study drug

Exclusions from randomized set, full analysis set, per-protocol set, [REDACTED]:

- Patient received study drug but was not randomized

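### The per-protocol set for the Week 26 endpoint has no time limit on on-treatment deviations, so a deviation after Day 184 can remove a valid Week 26 value

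*SAP*

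**What the plan says.** SAP 2.2 states that the PPS "will include all patients in the FAS who did not have any major protocol deviations". Protocol 9.1 has the same rule. Neither gives a date or visit limit, and SAP 16.1.9.2 makes clear that whole patients, not single visits, are excluded.

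The set has one use: "The PPS will be used for supportive analysis of the primary analysis only". SAP 2.6.1.4 adds that "the same MMRM used in the primary analysis will be also performed on the PPS". That model contains "visit (Days 2, 184, and 365" as visits, and the tested contrast is Day 184.

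The exclusion list in SAP 16.1.9.2 includes "OTH04: Patient receiving investigational drug other than study drug during the course of the study" and "COMD01: Banned asthma related Concomitant medication". The first spans the whole study and the second carries no date. OTH06 (compliance failure as judged by the investigator), WITH01 (too many exacerbations, treatment continued) and WITH02 (adolescent hospitalised for an exacerbation, treatment continued) are also undated.

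The primary analysis is run once every patient has reached Visit 207 or withdrawn. Its database holds 26 weeks of data for all patients and up to 52 weeks for completers (SAP 2.9.2). SAP 1 says "This SAP is valid for analyses of both CSRs".

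**The concern.** The primary estimand in SAP 2.1.1 asks for the effect had everyone stayed on assigned treatment through Week 26. Adherence after Day 184 has no bearing on that question. Under the rule as written, a patient who complied fully to Week 26 and first takes a banned asthma drug at Week 40 is dropped from the analysis of protocol adherers, and a valid Day 184 value goes with them.

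There are two consequences. First, membership depends on post-endpoint events that may themselves be influenced by treatment, so the selection could differ between arms. Second, it depends on enrolment date: at the data lock point an early enrollee has been open to exclusion for up to 52 weeks and a late one for about 26, so the same Week 40 deviation excludes one patient and not the other. If CSR II repeats the analysis, membership can change again for an endpoint whose data have not changed, after CSR I has been unblinded.

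**Working it through.** **1. The plan's own figure.** The documents state no number for the PPS, so the stated power serves as the check on the inputs. SAP 2.10 assumes a difference of 100 mL, SD 380 mL, 400 patients per arm and 10% dropout, giving n = 360 per arm.

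- SE = 380 × √(2/360) = 28.3 mL, and 100/28.3 = 3.53.
- Power per comparison at two-sided 0.05: Φ(3.53 − 1.96) = 94.2%. At 0.025: Φ(3.53 − 2.24) = 90.1%.
- Under the trimmed Simes procedure: 0.942 × 0.942 + 0.901 × (1 − 0.942) = 94.0%, against 94% stated. The figure reproduces.

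**2. Which codes can act after Week 26.** SAP 16.1.9.2 lists 39 codes that exclude from the PPS only. Read one by one, 34 (87%) are settled at entry, run-in or Day 1. Five (13%) can arise on treatment:

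| Code | Subject | Time limit |
|---|---|---|
| COMD01 | banned asthma medication | none |
| OTH04 | another investigational drug | whole study |
| OTH06 | compliance failure, investigator judgement | none |
| WITH01 | more than five exacerbations, still treated | none |
| WITH02 | adolescent hospitalised, still treated | none |

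**3. Possible shift in the PPS difference.** The documents give no rate of late deviations, so every rate and deficit below is an assumption. Let m and q be the shares of MF and QMF149 patients whose first on-treatment deviation falls after Week 26, and d the amount by which their Week 26 FEV1 lies below their arm's average. Removing them raises the MF mean by m·d/(1 − m) and the QMF149 mean by q·d/(1 − q). The QMF149 − MF difference therefore falls by m·d/(1 − m) − q·d/(1 − q).

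| m | q | d (mL) | Fall in difference (mL) |
|---|---|---|---|
| 3% | 1.5% | 150 | 4.64 − 2.28 = 2.4 |
| 4% | 2% | 200 | 8.33 − 4.08 = 4.3 |
| 6% | 3% | 250 | 15.96 − 7.73 = 8.2 |
| equal to q | equal to m | equal in both arms | 0 |

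The first three rows correspond to 12 to 24 MF and 6 to 12 QMF149 patients per 400. Against the SE of 28.3 mL, 2.4 to 8.2 mL is about 0.1 to 0.3 SE.

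For wider assumptions, let d be the deficit relative to the patients who remain, so that the fall is (m − q)·d. With m = 5%, q = 2% and d from 100 to 380 mL, it is 3 to 11 mL. With m = 10% and q = 5%, it is 5 to 19 mL.

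**4. Loss of precision.** If 2%, 5% or 10% of the 360 per arm were lost this way, n would be 353, 342 or 324. Power per comparison at two-sided 0.05 would be 93.8%, 93.1% or 91.8%, against 94.2% with no loss.

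**The case against.** Much of the opposing case stands.

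- **The PPS decides nothing.** The confirmatory tests use the full analysis set (SAP 2.6.1.2, 2.6.1.3), missing data have a separate tipping-point analysis, and reasons for exclusion from each set are tabulated (SAP 2.3.1).
- **A reader might infer that late exclusions are driven by exacerbations and so fall mainly on MF.** The documents do not support this. Only WITH01 and WITH02 concern exacerbations, and both also require that treatment was continued when Protocol 5.4.9 says it must stop. WITH02 is limited to adolescents, about 5% of 2000, or about 20 per arm. Protocol 5.4.8 permits otherwise prohibited drugs to treat an exacerbation, so COMD01 is not a proxy for one.
- **The assumed deficits are raw.** The model adjusts for baseline FEV1 and for both reversibility measurements, so 150 to 250 mL probably overstates what would move the contrast. With more exclusions under MF, the shift is also against QMF149 and so conservative for superiority.
- **A reader might infer that CSR I counts deviations to Week 52 for everyone, or that the PPS result is bound to differ between reports.** In CSR I the limit is the data lock point. Whether CSR II reruns the analysis is unclear: Protocol section 9 lists the primary objective there, while Protocol 9.6 and SAP 2.9.2 say that it is analysed only for CSR I.

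Two further replies are weaker. SAP 2.2 refers to a validation analysis plan, not supplied, that could contain dating rules. That possibility does not alter the rule stated in the SAP, and the SAP does not say whether the interim freeze or the final lock is meant. The Day 365 term in the model could justify dropping a late deviator's Day 365 value, but not the Day 184 value.

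**Conclusion.** The point holds in a limited form. The rule as written lets five of 39 PPS-only codes remove valid Week 26 values because of later events, and makes membership depend on enrolment date. That is a flaw in a stated rule for a set whose only purpose is to support the Week 26 result.

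Its size cannot be computed from the documents. It is zero if late-deviation rates and FEV1 deficits match between arms. It is about 2 to 8 mL if, as assumed, 3 to 6% of MF and 1.5 to 3% of QMF149 patients deviate late with a deficit of 150 to 250 mL. Neither the existence nor the direction of an imbalance is established. The confirmatory result is untouched. The case for change rests on the validity and reproducibility of the supportive analysis, not on any reversed conclusion.

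**What to change.** In SAP 2.2 and 16.1.9.2, state that COMD01, OTH04, OTH06, WITH01 and WITH02 exclude a patient from the Week 26 PPS only if the deviation began on or before that patient's Visit 207 trough (Day 184). Freeze the resulting set before the CSR I unblinding and reuse it unchanged in any CSR II rerun.

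Reconcile Protocol section 9, which lists the primary objective in CSR II, with Protocol 9.6 and SAP 2.9.2, which confine it to CSR I. Dating WITH01 also needs one agreed count: the code refers to more than five exacerbations, while Protocol 5.4.9 refers to five or more that required systemic corticosteroids. Those passages should be reconciled.

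The cost is one sentence in the SAP and a date condition in the program. The downside is that each on-treatment deviation needs an onset date, which may take some effort for OTH06 because it rests on investigator judgement. No new patient assessments are needed.
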